The Elders' Resilience Curriculum: Toward Building Empirical Evidence Around a Culturally-Grounded, Strengths-Based Intervention

clinicaltrials.gov ID:	NCT06045273
Protocol ID:	IRB00018615
U.S. NIH Grant/Contract	
Award Number:	K01MH122702
Principal Investigator:	[name] [name]
Document Date:	September 28, 2023
Included:	Study Protocol Statistical Analysis Plan (SAP) Informed Consent Form (ICF)

JHSPH IRB Research Protocol for Aim 3 New Data Collection

*Use this template for new data collection and if you also will analyze secondary data. Answer the questions below and for numbered sections that do not pertain to your study, retain the section numbers and bolded questions, and write "N/A." **DO NOT DELETE ANY QUESTIONS.** Please start typing in the gray boxes provided. You may delete this instruction box.*

PI Name: [name]

Study Title: The Elders' Resilience Curriculum: Toward Building Empirical Evidence Around a Culturally-Grounded, Strengths-Based Intervention

IRB No.: 00018615

PI Version No. / Date: 12 / 09/28/2023

I. Aims of the Study: Describe the aims/objectives of the research and/or the project's research questions or hypotheses.

The overall goal of this research is to better understand if and how the Elders' Resilience Curriculum (ERC), a culturally grounded, school-based program taught by White Mountain Apache Tribe (WMAT) Elders to youth, prevents suicide ideation and behaviors for American Indian youth. To achieve this goal, the study will utilize a mixed methods design. In **Aim 3**, we will work with White Mountain Apache tribal community partners to collaboratively design and pilot a rigorous evaluation, collecting quantitative data to test the ERC theoretical model and culturally adapted assessment battery.

Aim 3: To pilot ERC's theoretical model, culturally informed measures, and the feasibility and acceptability of a rigorous evaluation design to inform the development of a fully powered effectiveness study in a subsequent R01.

As of July 2023, we have collaborated with our White Mountain Apache tribal research partners to prepare and discuss an evaluation plan for Aim 3 which is outlined in the updates to this research plan version 6.

II. Background and Rationale: Explain why this study is being done. Summarize briefly what is already known about the issue and reference previously published research, if relevant.

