A. Provide a BRIEF overview of your study design and methods. The study design must relate to your stated aims/objectives. DETAILS WILL BE REQUESTED LATER. *If your study also involves analysis of existing data, please complete Section XI, "Secondary Data Analysis of Existing Data" in the last part of this research plan. If your study ONLY involves analysis of existing data, please use the research plan template for secondary data analysis (JHSPH IRB Research Plan for Secondary Data Analysis of Existing Data/Specimens)*

Aim 3

Aim 3 of the project includes a pre-/post-test design evaluation of the Elders' Resilience

Curriculum using culturally adapted measures. The ERC is a monthly curriculum delivered by Elders to youth in classrooms. Delivery of ERC curriculum content will be monitored by WMAT CMHSs using session summary sheets. The PI and a research assistant will check session summary sheets to check if core components were delivered with fidelity and to compare against core components determined in Aim 1.

A survey comprised of these culturally adapted measures will be administered to youth in schools where the ERC is delivered at three timepoints – once at the beginning of the school year, once during the middle of the school year, and finally at the end of the school year. Change in outcomes over time as students receive the ERC lessons will be assessed.

B. Provide a sample size and a justification as to how you arrived at that number. If you use screening procedures to arrive at a final sample a table may be helpful.

Aim 3

For the pre-/post-test survey in Aim 3 we will aim to recruit and enroll up to $N=200$ youth ages 9-14 from 5-10 classrooms where the ERC is delivered. This sample size is based on feasibility and convenience (e.g., based on the classroom sizes in schools where the ERC is delivered) and leaves flexibility in case classroom sizes are larger than anticipated.

IV. Participants:

Describe the study participants and the population from which they will be drawn. Specify the inclusion and exclusion criteria. If you plan to include children, note their ages and whether you will include children in foster care. Note if the participants are particularly vulnerable in terms of cognitive limitations, education, legal migration status, incarceration, poverty, or some combination of factors.

A. Inclusion Criteria:

Aim 3:

Inclusion criteria for participants in the pre/post study:

- 1) Be between 9-14 years of age

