2. Identify the countries where the research will take place, and the languages that will be used for the consent process.

Country	Consent Document(s) (Adult Consent, Parental Permission, Youth Assent, etc.)	Languages
United States	Adult Consent	English
United States	Parental Permission	English
United States	Youth Assent	English
United States	Youth Assent – Aim 3 Survey	English
United States	Parent Passive Permission – Aim 3 Survey	English
United States	Youth Assent – Aim 3 Cognitive Interview	English
United States	Caregiver Permission – Aim 3 Cognitive Interview	English

C. **Study Implementation:**

1. Describe the procedures that participants will undergo. If complex, insert a table below to help the reviewer navigate.

Aim 3:

Survey: Students will be asked to complete a paper survey containing the measures outlined below in the table below. The paper survey will be a hard copy document. Study staff will be available to answer questions and support students in completing the survey (e.g., if they do not understand what a question is asking, staff will help explain further). Students will be asked to complete this survey at three timepoints (see answer to #2 below and table) and will complete the surveys in their classrooms. The study team will work with classrooms and schools to schedule an appropriate time to go into the classroom during school and administer the survey.

Measure	Outcome(s) measure will assess	Frequency		
		Baseline (August 2023)	Midline (January 2024)	Endline (May 2024)
Demographics	Demographics	X		
Index of local indicators of well- being	Physical Health, Emotional Health, Social Health, Community Connectedness	X	X	X
Apache language questions	Apache language skills	X	X	X

Awareness of Connectedness scale	Community Connectedness, Family Connectedness	X	X	X
Cultural Connectedness Scale – Short form	Spiritual Health, Identity, Cultural continuity	X	X	X
Cultural Efficacy scale	Identity, Cultural continuity	X	X	X
Group level self-identification and self-investment	Identity, Belonging	X	X	X
Intergenerational Connectedness scale	Intergenerational Connectedness: youth and Elders being able to connect Intergenerational Connectedness: youth feeling connected to past, present, and future	X	X	X
Multicultural mastery scale	Emotional Health, Mental Health, Social Health, Community Connectedness, Family Connectedness	X	X	X
Reasons for life scale	Mental Health, Spiritual Health	X	X	X
Rosenberg self-esteem scale	Mental Health	X	X	X

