The overall goal of the analysis will be to assess for change in outcomes across time from all three survey timepoints (baseline, midline, and endline) using a pre/post analysis. All responses will be analyzed with SPSS software to examine internal consistency of each scale, item and scale level response distributions, inconsistencies in responses, and missing data patterns. Change over time in key outcomes (see table above listing outcomes) will be assessed. Session summary forms will be reviewed to assess intervention delivery fidelity and consistency across lessons. Cognitive interview responses will be compiled and analyzed to assess item fit and comprehension and to make potential improvements or changes to future surveys.

The original plan was to run an Observed Change Score Model where we created difference scores from baseline to midline and midline to endline and examined which predictors explained changes during those two periods.

After running these models using SEM, the models were unstable and therefore the results were biased and untrustworthy. Thus, I pivoted to conducting a Linear Mixed Model or Mixed Effects Model that could account for the repeated measures structure with only one group and allows participants to vary at baseline. Due to the number of participants in the data set, I wasn't confident that this model would run when first deciding on a model, but it ended up running without issue. I checked the assumptions for running the model with our data and all of the assumptions were met. The assumptions are:

Linearity: Check with residuals vs predictors.

Independence: Accounted for by random effects but plotted residuals over time to check.

Homoscedasticity: Plot residuals vs fitted values.

Normality of Residuals: Histogram and Q-Q plot of residuals.

Normality of Random Effects: Plot random intercept distribution.

The equation for the model is as follows

$$RFL = \beta_0 + \beta_1 Midline + \beta_2 Endline + \beta_3 AWOC + \beta_4 CCS + \beta_5 CCS ID + \beta_6 CES + \beta_7 LWI + \beta_8 IC + \beta_9 MMS + \beta_{10} RES + \beta_{11} SDI + u_i + e_{ij}$$

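### The stated goal is change over time in the key outcomes, but the only current equation adjusts the RFL time terms for nine scores of unstated timing, and no time-only model is written

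*Combined protocol and SAP*

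**What the plan says.** The SAP (Aim 3, first paragraph) gives its goal as change in outcomes "across time from all three survey timepoints (baseline, midline, and endline) using a pre/post analysis", and adds: "Change over time in key outcomes (see table above listing outcomes) will be assessed". Protocol section III.A says the same: "Change in outcomes over time as students receive the ERC lessons will be assessed". The table referred to is in protocol section V.C.1. It lists twelve measures repeated at baseline, midline and endline, under the column "Outcome(s) measure will assess". The SAP does not say which of them are key.

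The planned change-score model, which "examined which predictors explained changes during those two periods", was dropped as unstable. A linear mixed model replaced it, and the SAP reports that "it ended up running without issue". The one equation given is "RFL = \beta_0 + \beta_1 Midline + \beta_2 Endline + \beta_3 AWOC + \beta_4 CCS + \beta_5 CCS ID", followed by CES, LWI, IC, MMS, RES and SDI, a random intercept and a residual.

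The abbreviations are not defined. By their initials, the nine scores come from eight other measures in the same table, with CCS and CCS ID from one scale. Three repeated measures (Apache language, academic outcomes and health ratings) appear in no equation.

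**The concern.** A change goal needs an estimate of mean RFL at endline minus mean RFL at baseline, and the same for midline. A time coefficient adjusted for same-wave scores answers another question: how far RFL differs between waves at fixed values of the other nine scores. If the curriculum moves those scores and they are related to RFL, part of the RFL change is assigned to them and leaves the time terms.

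No model containing only time is written for RFL, and none at all for any other key outcome. A reader cannot tell which estimates will be reported as change. That matters because section I gives the purpose of Aim 3 as informing a fully powered effectiveness study. A conditional time term taken for RFL change could misdirect its planning.

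**Working it through.** The plan states no effect size, SD, correlation or power, so there is no figure of its own to reproduce.

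**Counts.** Score terms run from β3 to β11, which is 9. Repeated measures: RFL + 8 apparently in the equation + 3 in no equation = 12.

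**Timing.** The only subscripts are on the random intercept and the residual. RFL itself has none, so their absence from the scores proves nothing. Same-wave entry is plausible because every scale is collected at each wave and none is labelled baseline. There is also no score-by-time interaction, so baseline scores could relate to RFL level but could not explain change.

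**Algebra.** With complete data, wave indicators and a random intercept, the residuals average zero at each wave:

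- endline: mean RFL = β0 + β2 + Σ βk × (mean score k at endline)
- baseline: mean RFL = β0 + Σ βk × (mean score k at baseline)

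Subtracting gives β2 = mean RFL change − Σ βk × (mean change in score k). The same holds for β1 at midline. If the scores are fixed at baseline, their change is zero and β2 is mean RFL change.

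**Illustration (every input assumed).** True RFL gain is 0.30 SD. Nine scores have pairwise correlation r, and each has correlation q with RFL. Each standardised slope is then b = q/(1 + 8r). If m scores rise by d, the Endline term is 0.30 − m × b × d.

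At r = q = 0.4, b = 0.4/4.2 = 0.095:

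- three rise 0.20: 0.30 − 3 × 0.095 × 0.20 = 0.243
- all nine rise 0.10: 0.30 − 9 × 0.095 × 0.10 = 0.214
- scores flat: 0.30

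At r = 0.4, q = 0.3 gives b = 0.071 and Endline terms of 0.257 and 0.236. At q = 0.5, b = 0.119 and the terms are 0.229 and 0.193.

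**Coverage of the true 0.30 by the 95% CI of the same-wave Endline term.** Simulated with a REML random-intercept model, three waves, complete data, intraclass correlation 0.5, midline shift half the endline shift, and r = 0.4. N = 200 is the protocol's upper limit and N = 100 is assumed. Ranges are the spread over repeated simulations.

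| q | Scores that rise | N=100 | N=200 |
|---|---|---|---|
| 0.3 | three by 0.20 | 91–92% | 90–91% |
| 0.3 | nine by 0.10 | 90% | 79–83% |
| 0.4 | three by 0.20 | 90–91% | 84% |
| 0.4 | nine by 0.10 | 81–83% | 67–69% |
| 0.5 | three by 0.20 | 82–83% | 67–70% |
| 0.5 | nine by 0.10 | 65–67% | 39–42% |

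The time-only model covered 0.30 in about 94–96% of runs throughout, as did the nine-score model with flat scores. Coverage of the same-wave term generally falls as N grows, because the interval narrows around a different quantity.

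**The case against.** The strongest reply is that this is a predictor model and its time terms are nuisance terms. Section I gives the purpose as "collecting quantitative data to test the ERC theoretical model and culturally adapted assessment battery", and the dropped model also asked about predictors. On that reading the equation fits its purpose and its conditional estimates are valid. This stands. It leaves the SAP's own change goal without a written model.

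It is also fair that key outcomes may be a subset, that the abbreviations are matched by inference, and that this is an uncontrolled pilot sized by feasibility.

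Three stronger readings are tempting, and none is supported:

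- **That the SAP misreports RFL change.** Nothing in it says the Midline and Endline terms will be read as change, and score timing is not stated.
- **That RFL change is understated whenever the other scores rise.** The shift is a weighted sum of partial slopes. With correlated scores some slopes can be zero or negative, so the shift can be nil or upward.
- **That the analysis loses its power or reverses the sign.** With three scores rising 0.20 and q = 0.5, the Endline term was significant in 90% of runs at N = 100, against 85% for time-only. A reversal needs extreme inputs. With all nine rising 0.30, the term is 0.30 − 9 × 0.119 × 0.30 = −0.02 at q = 0.5, but 0.30 − 9 × 0.095 × 0.30 = +0.04 at q = 0.4.

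**Conclusion.** The concern holds in conditional form and should be fixed. Two things are certain from the text: the timing of the nine scores is not stated, and the change goal is tied to no written model, for RFL or any other key outcome.

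If the scores are same-wave, the time terms are RFL change only when the weighted sum of score changes is zero. Understatement is the expected direction if the protective factors rise and are positively related to RFL, as the programme intends. Under mid-range assumptions the loss is about 0.06 to 0.09 SD of a 0.30 SD gain. These sizes rest wholly on assumed correlations and changes, equal positive slopes and complete data.

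With baseline-only scores the problem with the time terms disappears, exactly so only if data are complete. The missing change model remains either way.

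**What to change.** - Add a mixed model for RFL with Midline, Endline and a random intercept only. Report its two changes from baseline with 95% CIs as the estimate of RFL change, labelled post hoc because models have already been run.
- Name the other key outcomes and do the same for each, with a model suited to how that outcome is scored. The documents do not give scoring rules for the academic and health items, so these need to be stated first.
- Keep the nine-score equation as a separate analysis of association with RFL under the theoretical model. Define its abbreviations and state the timing of its scores. If they are same-wave, say that its Midline and Endline terms are not change in RFL.

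The cost is SAP wording and extra models on the survey data, with no new data collection. The downside is more post hoc estimates. RFL and the nine scores alone would give 10 × 2 = 20 changes, with more if the other three measures are key and fewer if a subset is named. They should be presented as exploratory, without multiplicity-controlled claims.

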Self-reported academic outcomes	Academic outcomes	X	X	X
Self-reported health ratings	Physical Health, Mental Health, Spiritual Health	X	X	X

Measure	Description
Index of local indicators of well-being	18 self-report items developed by our White Mountain Apache Tribe (WMAT) collaborators for a previous research study [9] and for this study. These items capture positive impacts among WMAT youth related to suicide prevention interventions, including the Elders' Resilience Curriculum.
Apache language questions	5 questions developed by our WMAT collaborators assess Apache language skills.
Awareness of Connectedness scale	The Awareness of Connectedness Scale [10] is a 12-item self-report measure that evaluates awareness of connection with self, family, community, and the natural environment. This scale has been used in previous research with WMAT youth [11, 12].
Cultural Connectedness Scale – Short form	The Cultural Connectedness Scale-short version [13] is a 9-item self-report measure that assesses connection to cultural identity, traditions, and spirituality among First Nations youth. This measure has been used in previous research with AIs [14].
Cultural Efficacy scale	5 self-report items measure cultural efficacy and are sourced from a research study with AI participants [15].
Group level self-identification and self-investment	6 self-report items that capture solidarity, satisfaction, centrality, individual self-stereotyping, and in-group

	homogeneity [16]. Items from this scale have been used in previous research with AI adolescents to assess cultural identification [17].
Intergenerational Connectedness scale	7 items developed through another ongoing study assess intergenerational connectedness.
Multicultural mastery scale	The Multicultural Mastery Scale for youth [18] includes 13 self-report items that were retained and adapted for use in the local WMAT context by [9] in another research study. Items in this measure assess mastery in relation to self and community. The original measure has been used with American Indian youth in previous research [18].
Reasons for life scale	11 self-report items from the Reasons for Life scale [19] measure beliefs and experiences that make youth feel like life is enjoyable, worthwhile, and meaningful. It was adapted from an adolescent measure of brief reasons for living [20] for use in research with Alaska Native youth and has been used in other research with AIs [18].

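### Does entering both CCS and CCS ID in the mixed model make the CCS ID coefficient misleading?

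*Combined protocol and SAP*

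**What the plan says.** The Statistical Analysis Plan (Aim 3) replaces an unstable change-score model with a "Linear Mixed Model or Mixed Effects Model that could account for the repeated measures structure with only one group". The outcome is RFL, evidently the Reasons for Life measure, described in protocol section V.C.1 as "11 self-report items from the Reasons for Life scale". The fixed effects are two time indicators (midline and endline) and nine scale terms, among them "\beta_4 CCS + \beta_5 CCS ID + \beta_6 CES". The plan expands none of the abbreviations in the equation and gives no scoring rule (sum or mean).

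Section V.C.1 lists one Cultural Connectedness Scale, the short form, as a "9-item self-report measure that assesses connection to cultural identity, traditions, and spirituality among First Nations youth". The measures table in the same section gives its outcomes as "Spiritual Health, Identity, Cultural continuity". Neither place describes an identity subscale or says how many of the nine items concern identity.

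Section I states that Aim 3 is a pilot, "collecting quantitative data to test the ERC theoretical model and culturally adapted assessment battery". Section III.B sets the ceiling on enrolment: "recruit and enroll up to $N=200$ youth ages 9-14 from 5-10 classrooms where the ERC is delivered".

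**The concern.** Each of the other scales appears once in the equation, under one abbreviation. The Cultural Connectedness Scale seems to appear twice, as CCS and as CCS ID. By that pattern the plain label would be the whole scale and the second label its identity part, so the identity items would be counted in both terms.

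On that reading, β5 does not answer the question that a reader would put to it. A β5 near zero would mean that identity items and the other items relate to RFL about equally, not that identity is unrelated to RFL. A negative β5 would mean that identity's slope is the smaller of the two, not that identity goes with lower RFL. Identity is one of the constructs that the study sets out to measure, and the scale coefficients may be read as a test of the theoretical model. A results table taken at face value could therefore give the wrong message about it.

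**Working it through.** The documents give no figure on this point, so there is nothing of the plan's own to reproduce. The check is algebra, confirmed on simulated data.

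**Inputs from the documents.** Nine items in the scale (section V.C.1); CCS and CCS ID as separate fixed effects in a random-intercept model with three timepoints (Statistical Analysis Plan).

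**Assumptions the documents neither confirm nor exclude.** CCS is the nine-item total T. CCS ID is the score I on k identity items. R is the score on the other 9 − k items.

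**Sum scores.** T = I + R, so

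β4·T + β5·I = (β4 + β5)·I + β4·R.

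The slope of the other items is β4, identity's slope is β4 + β5, and β5 is identity's slope minus the slope of the other items.

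**Mean scores.** T = [k·I + (9 − k)·R]/9, so

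β4·T + β5·I = [(k/9)β4 + β5]·I + [(9 − k)/9]β4·R.

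Identity's slope is (k/9)β4 + β5, the remainder slope is [(9 − k)/9]β4, and β5 is identity's slope minus k/(9 − k) times the remainder slope. The plain difference therefore holds for sum scores only. Worked example with k = 3, β4 = 0.573, β5 = 0.137:

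- identity: (3/9)(0.573) + 0.137 = 0.191 + 0.137 = 0.328
- remainder: (6/9)(0.573) = 0.382, which is not β4
- check: 0.328 − (3/6)(0.382) = 0.137 = β5

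**Numerical check.** Random-intercept models were fitted to simulated data (200 participants, three timepoints), one data set for each of 16 scenarios: k = 2, 3, 4, 5 crossed with four pairs of true slopes. Results for k = 3 with sum scores (last digits are rounded):

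| True slopes (identity / other) | Fitted identity | Fitted other = β4 | β5 |
|---|---|---|---|
| 0.3 / 0.3 | 0.2876 | 0.2959 | −0.0083 |
| 0.3 / 0 | 0.3301 | −0.0215 | 0.3516 |
| 0.3 / 0.5 | 0.2373 | 0.5355 | −0.2982 |
| 0 / 0.3 | 0.0716 | 0.2983 | −0.2266 |

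The identities held in all 16 scenarios under both scorings.

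**What is left unchanged.** Only one subscale accompanies the total, so there is no exact collinearity. The pair (T, I) and the pair (I, R) span the same predictors. Fit, time effects and the other seven scale coefficients are therefore the same. In a larger simulation with all the scale terms, β4 + β5 matched identity's slope from the non-overlapping model, and the midline coefficients of the two models matched, to within 3e-8 in every data set compared.

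**How often β5 would mislead.** This depends on inputs that the documents do not give. The larger simulation assumed correlations of 0.3 to 0.7 between parts of the scale, three complete waves, and chosen slopes and variances, with sum scores:

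- Both slopes 0.2: β5 was significant in about 5% of data sets. That follows by construction, because the difference tested is zero.
- Identity 0.1, other 0.2: β5 was significantly negative in 16–29% (N = 100) and 26–50% (N = 200).
- Identity 0, other 0.2: 44–81% and 73–97%.

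The last two lines are the power to detect a difference that was put in by assumption. They show that the misreading is possible and do not estimate its chance in this trial. The value 200 is the enrolment ceiling, 100 has no source in the documents, and the plan does not state the number analysed.

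**The case for a change.** The strongest case for a change is that the text needs a remedy on either reading. If CCS leaves out the identity items, one sentence would say so. If it includes them, the CCS ID row needs re-expressing, at the cost of one linear contrast from the fitted model. The abbreviation pattern favours the overlapping reading, the algebra is exact, and nothing in the plan warns a reader of the results.

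The algebra stands, and so does the absence of definitions. The rest does not carry to a change in the plan. Two labels for one instrument fit a split into identity items and remaining items as well as they fit a total plus a part. On the split, β5 is the ordinary adjusted slope. The step that is needed on either reading is only to expand an abbreviation, and the other labels in the equation are unexpanded too. The plan reports that the model has been fitted, so the score definitions exist in the data set.

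Nor does the plan commit itself to a reading of β5. Its stated analysis goal is change over the three timepoints, which this question does not touch. On the overlapping reading, β5 is still a valid test of whether identity items relate to RFL differently from the other items.

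Re-expressing the coefficient would also gain less than it seems. β4 + β5 would still be adjusted for CES and, apparently, SDI, and the measures table in section V.C.1 lists the corresponding scales under identity as well. It would be a partial coefficient, not identity's overall association with RFL.

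**Conclusion.** No change to the plan follows. The gap is two undefined labels and an unstated scoring rule, which an analyst fills when describing the scores. The possible harm is confined to reading the CCS and CCS ID rows, and it arises only if CCS includes the identity items, which the documents leave open. In that case β5 is a contrast between the identity items and the rest. Identity's slope can be had exactly from the fitted model: β4 + β5 for sum scores, (k/9)β4 + β5 for mean scores, with a standard error from the coefficient covariance matrix. Fit, time effects and all other coefficients are the same on either parameterisation. The simulated percentages rest on assumed slopes, variances and correlations, and are not evidence of impact in this trial.
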